#### 4.1.3. Exclusion Criteria

Deviations from exclusion criteria are not allowed because they can potentially jeopardize the scientific integrity of the study, regulatory acceptability or subject safety. Therefore, adherence to the criteria as specified in the protocol is essential.

Subjects meeting any of the following criteria must not be enrolled in the study:

1. Neurological symptoms related to brain metastasis that are not controlled with a stable or decreasing dose of oral steroids for at least 7 days prior to starting study treatment.
2. Prior whole brain radiation (WBRT). Prior treatment with stereotactic radiosurgery is permitted so long as there is one evaluable lesion which has not been treated with SRS.
3. Previous treatment with a BRAF or MEK inhibitor.
4. Cancer therapy (chemotherapy with delayed toxicity, extensive radiation therapy, immunotherapy, biologic therapy, or major surgery) or investigational anti-cancer

drugs within the last 3 weeks, or chemotherapy without delayed toxicity within the last 2 weeks, preceding the first dose of study treatment.

5. Current or expected use of a prohibited medication as described in Section 6.2, including enzyme-inducing antiepileptic drugs (EIAEDs) during treatment with dabrafenib.
6. Presence of leptomeningeal disease or dural metastases.
7. History of another active malignancy within the past 5 years, or any malignancy with a confirmed activating RAS mutation. Please note prospective RAS mutation testing is not required, however, if results of previous RAS testing are known, they must be used in assessing eligibility. Subjects with a history of completely resected non-melanoma skin cancer are eligible.
8. Known allergies against contrast agents required for MRI of intracranial lesions, or other contraindications for MRI, i.e., pacemaker.
9. Current use of therapeutic warfarin. Low-molecular-weight heparin and prophylactic low-dose warfarin are permitted.
10. Unresolved toxicity of National Cancer Institute Common Terminology Criteria for Adverse Events, version 4.0 (CTCAE v4.0) [NCI, 2009] Grade 2 or higher from previous anti-cancer therapy, except alopecia.
11. Presence of active gastrointestinal disease or other condition that will interfere significantly with the absorption of drugs.
12. History of a prior symptomatic stroke, dementia, or other significant central neurologic condition (i.e. multiple sclerosis).

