## 5.7.6. Liver Chemistry Stopping and Follow-Up Criteria

### 5.7.6.1. Liver Chemistry Stopping Criteria

These liver chemistry stopping and follow up criteria have been designed to assure subject safety and evaluate liver event aetiology in alignment with the FDA Guidance for Industry – Drug-Induced Liver Injury: Premarketing Clinical Evaluation (July 2009, [www.fda.gov](http://www.fda.gov)).

Phase II liver chemistry stopping criteria 1-5 are defined as follows:

1. Alanine aminotransferase (ALT)  $\geq 3xULN$  **and** bilirubin  $\geq 2xULN$  (>35% direct bilirubin) (or ALT  $\geq 3xULN$  and international normalized ratio (INR)  $>1.5$ , if INR measured)

**NOTE:** If serum bilirubin fractionation is not immediately available, study drug should be discontinued if ALT  $\geq 3xULN$  **and** bilirubin  $\geq 2xULN$ . Serum bilirubin fractionation should be performed if testing is available. If testing is not available, **record presence of detectable urinary bilirubin on dipstick**, indicating direct bilirubin elevations and suggesting liver injury.

2. ALT  $\geq 5xULN$
3. ALT  $\geq 3xULN$ , if associated with symptoms (new or worsening) believed to be related to hepatitis, such as fatigue, nausea, vomiting, right upper quadrant pain, tenderness or jaundice), or hypersensitivity (such as fever, rash or eosinophilia).
4. ALT  $\geq 3xULN$  persists for  $\geq 4$  weeks
5. ALT  $\geq 3xULN$  and cannot be monitored weekly for 4 weeks.

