**When any of the liver chemistry stopping criteria 1 - 5 is met, do the following:**

- **Immediately discontinue** investigational product
- Report the event to GSK within **24 hours** of learning its occurrence
- Complete the liver event case report form (CRF) and serious adverse event (SAE) data collection tool if the event also meets the criteria for an SAE
  - All events of ALT  $\geq 3xULN$  **and** bilirubin  $\geq 2xULN$  (>35% direct bilirubin) (or ALT  $\geq 3xULN$  and INR  $>1.5$ , if INR measured; INR measurement is not required and the threshold value stated will not apply to subjects receiving anticoagulants), termed ‘Hy’s Law’, **must be reported as an SAE (excluding studies of hepatic impairment or cirrhosis)**.
  - **NOTE:** If serum bilirubin fractionation is not immediately available, and if ALT  $\geq 3xULN$  **and** bilirubin  $\geq 2xULN$ , discontinue subject from study treatment. Serum bilirubin fractionation should be performed if testing is available. If testing is unavailable, **record presence of detectable urinary bilirubin on dipstick**, indicating direct bilirubin elevations and suggesting liver injury

- Complete the liver imaging and/or liver biopsy CRFs (provided by GSK) if these tests are performed
- Perform liver event follow up assessments, and monitor the subject until liver chemistries resolve, stabilize, or return to baseline values as described below
- Withdraw the subject from the study (unless further safety follow up is required) after completion of the liver chemistry monitoring as described below.
- For studies where survival or progression is an endpoint, follow-up for overall survival or progression is required following discontinuation from study treatment.
- Do not rechallenge with investigational product.

In addition, for subjects meeting liver stopping criterion 1:

- Make every reasonable attempt to have subjects return to clinic **within 24** hours for repeat liver chemistries, liver event follow up assessments (refer to Section 5.7.6.3), and close monitoring
- A specialist or hepatology consultation is recommended
- Monitor subjects twice weekly until liver chemistries (ALT, AST, alkaline phosphatase, bilirubin) resolve, stabilize or return to within baseline values.

In addition, for subjects meeting any of the criteria 2 - 5:

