#### 5.7.6.2. Liver Chemistry Monitoring Criteria

For subjects with ALT  $\geq 3 \times \text{ULN}$  but  $< 5 \times \text{ULN}$  and bilirubin  $< 2 \times \text{ULN}$ , without hepatitis symptoms or rash, and who can be monitored weekly for 4 weeks, the following actions should be taken:

- Notify the GSK Medical Monitor within 24 hours of learning of the abnormality to discuss subject safety
- Continue study treatment
- Return weekly for repeat liver chemistries (ALT, AST, alkaline phosphatase, bilirubin) until they resolve, stabilize or return to within baseline
- If at any time the subject meets any of the liver chemistry stopping criteria 1 – 5, proceed as described above
- If, after 4 weeks of monitoring, ALT  $< 3 \times \text{ULN}$  and bilirubin  $< 2 \times \text{ULN}$ , monitor subjects twice monthly until liver chemistries normalize or return to within baseline values.

Refer to [Appendix 3](#) for an algorithm of liver chemistry monitoring, interruption, stopping and follow-up criteria.

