## **6. CONCOMITANT MEDICATIONS AND NON-DRUG THERAPIES**

### **6.1. Permitted Medications and Non-Drug Therapies**

The investigator must be informed as soon as possible about any medication taken from the time of screening until 30 days after the last dose of study treatment. Any concomitant medication(s), including dietary supplements, taken during the study will be recorded in the eCRF. The minimum requirement is that drug name, dose, and the dates of administration are to be recorded. Additionally, a complete list of all prior surgical procedures will be recorded in the eCRF.

Subjects should receive full supportive care during the study, including transfusions of blood and blood products, and treatment with antibiotics, anti-emetics, anti-diarrheals, and analgesics, and other care as deemed appropriate, and in accordance with their institutional guidelines. Use of anticoagulants such as warfarin is permitted provided that INR is monitored in accordance with local institutional practice.

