### 6.3. Medications to be Used with Caution

The following medications should be used with caution as their concentrations may be altered by dabrafenib or they may alter dabrafenib concentrations:

- Drugs that are moderate inhibitors or inducers of CYP3A and CYP2C8 as they may alter concentrations of dabrafenib.
- Dabrafenib has been shown to induce CYP3A4 and CYP2C9 in vivo using midazolam (CYP3A4 substrate) and S-warfarin (CYP2C9 substrate). Dabrafenib is an in vitro inducer of CYP2B6 and other enzymes such as CYP2C8, CYP2C19, UDP-glucuronyl transferases. Transporters may also be affected. Co-administration of dabrafenib and medications which are affected by the induction of these enzymes (including warfarin) and transporters may result in loss of efficacy. If co-administration of these medications is necessary, investigators should monitor subjects for loss of efficacy or consider substitutions of these medications. A partial list of these medications is provided in [Table 18](#) and in the SPM.
- Therapeutic level dosing of warfarin can be used with approval by the GSK Medical Monitor and close monitoring of PT/INR by the site. Exposure decreased by 37% due to enzyme induction when on treatment, thus warfarin

dosing may need to be adjusted based upon PT/INR. Consequently, when discontinuing dabrafenib, warfarin exposure may be increased and thus close monitoring via PT/INR and warfarin dose adjustments must be made as clinically appropriate. Prophylactic low dose warfarin may be given to maintain central catheter patency.

- Dabrafenib solubility is pH-dependent with decreased solubility at higher pH. Drugs such as proton pump inhibitors that inhibit gastric acid secretion to elevate gastric pH may decrease the solubility of dabrafenib and reduce its bioavailability. No clinical study has been conducted to evaluate the effect of pH on dabrafenib pharmacokinetics. In an ad-hoc analysis, no differences in  $C_{\max}$  and AUC were noted between subjects who reported taking pH-elevating products relative to other subjects. Due to the theoretical risk that pH-elevating agents may decrease oral bioavailability and exposure to dabrafenib, these medicinal products that increase gastric pH should be used with caution when administered with dabrafenib.

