| Liver chemistry abnormalities Phase II:                                                                            |                       |                                                                                                                                               |                                            |                                                                        |
| ALT $\geq$ 3xULN and bilirubin $\geq$ 2xULN (>35% direct) (or ALT $\geq$ 3xULN and INR>1.5, if INR measured)  | 24 hours  | SAE data collection tool. Liver Event Case Report Form (CRF) and liver imaging and/or biopsy CRFs if applicable                   | 24 hours                                   | Updated SAE data collection tool. Updated Liver Event CRF  |
| ALT $\geq$ 5xULN; ALT $\geq$ 3xULN with hepatitis or rash or 3xULN $\geq$ 4 weeks                                         | 24 hours  | Liver Event CRF                                                                                                                   | 24 hours                                   | Updated Liver Event CRF                                    |
| ALT $\geq$ 3xULN and <5xULN and bilirubin <2xULN                                                                          | 24 hours  | Liver Event CRF does not need completing unless elevations persist for 4 weeks or subject cannot be monitored weekly for 4 weeks  |                                            |                                                                        |

1. GSK to be notified at onset of liver chemistry elevations to discuss subject safety.
2. Liver Event Documents (i.e., "Liver Event CRF" and "Liver Imaging CRF" and/or "Liver Biopsy CRF", as applicable) should be completed as soon as possible
3. INR measurement is not required; if measured, the threshold value stated will not apply to subjects receiving anticoagulants.

Please refer to the liver chemistry stopping rules and follow-up criteria in Section [5.7.6](#) for additional details.

Methods for detecting, recording, evaluating, and following up on AEs and SAEs and procedures for completing and transmitting SAE reports to GSK are provided in the SPM. Procedures for post-study AEs and SAEs are provided in the SPM.

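### Liver stopping criterion 1 omits the anticoagulant exemption that the protocol attaches to the same INR limb everywhere else in its visible text, so a narrow group is stopped for good instead of monitored.

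*Protocol*

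**What the plan says.** Protocol Section 5.7.6.1 lists five liver stopping criteria. Criterion 1 has two limbs: ALT ≥3×ULN with bilirubin ≥2×ULN, or ALT ≥3×ULN "and international normalized ratio (INR) $>1.5$ , if INR measured". The note beneath it concerns bilirubin fractionation only. Meeting any of criteria 1–5 means immediate discontinuation without rechallenge, and Section 4.2 bars retreatment after permanent discontinuation.

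The INR limb appears three more times, each time with an exemption:

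- In the action list that follows the five criteria, the sub-bullet on which events must be reported as SAEs adds "INR measurement is not required and the threshold value stated will not apply to subjects receiving anticoagulants".
- Section 7.3.1.2, on protocol-specific SAEs, repeats those words.
- Section 7.3.1.6, footnote 3 to the reporting table, says "INR measurement is not required; if measured, the threshold value stated will not apply to subjects receiving anticoagulants".

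Section 5.7.6.2 covers subjects with ALT from 3 to below 5×ULN and bilirubin below 2×ULN, "without hepatitis symptoms or rash, and who can be monitored weekly for 4 weeks". They continue study treatment with weekly liver chemistries unless they come to meet one of criteria 1–5. The section has no INR condition.

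On anticoagulants, exclusion criterion 9 (Section 4.1.3) bars "Current use of therapeutic warfarin. Low-molecular-weight heparin and prophylactic low-dose warfarin are permitted". Once on study, Section 6.1 says "Use of anticoagulants such as warfarin is permitted provided that INR is monitored in accordance with local institutional practice", and Section 6.3 says "Therapeutic level dosing of warfarin can be used with approval by the GSK Medical Monitor and close monitoring of PT/INR by the site".

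**The concern.** Three of the four visible statements of this limb set the INR threshold aside in anticoagulated subjects. The one that does not is the one that ends treatment. The same laboratory values can therefore force permanent discontinuation while not counting as a Hy's Law SAE.

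The condition that INR be measured does not remove the problem. Table 19 schedules coagulation tests only at screening and on the day before surgery. After surgery, Sections 6.1 and 6.3 still require INR monitoring in warfarin subjects, so the limb is open to them by routine, while other subjects have no scheduled INR.

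ALT ≥3×ULN is a liver signal in its own right. In this band, however, the protocol's stated response to it is weekly monitoring on treatment. The step up to permanent stopping comes only from an INR that the protocol elsewhere says does not count. The loss cannot be reversed, in a disease for which Section 1.1 gives a median survival of 2.8 to 4 months.

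**Working it through.** The plan gives no figure to reproduce, so the check compares the four statements of the limb and then traces one case through the rules.

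**The four statements**

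| Place | Purpose | ALT ≥3×ULN with INR >1.5 | Anticoagulant exemption |
|---|---|---|---|
| 5.7.6.1, criterion 1 | Stop treatment | Yes | No |
| 5.7.6.1, SAE sub-bullet | Classify as SAE | Yes | Yes |
| 7.3.1.2 | Define SAE | Yes | Yes |
| 7.3.1.6, footnote 3 | Report to sponsor | Yes | Yes |

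**Does the sub-bullet amend criterion 1?** It sits in a list that applies once a stopping criterion has been met, and the first action in that list is discontinuation. The exemption is reached only after the stop has been triggered, and it qualifies which events are reported as SAEs. It does not change criterion 1.

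**Can the case arise?** Exclusion criterion 9 bars therapeutic warfarin at entry. Table 2 footnote a suggests another entry route for anticoagulated subjects, but nothing here relies on it. The route used is warfarin started on study under Sections 6.1 and 6.3.

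**Traced case.** Assumed values: on warfarin, INR 2.5, ALT 4×ULN, bilirubin 1×ULN, no symptoms, first elevation, weekly monitoring possible.

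| Criterion | Test | As written | With exemption |
|---|---|---|---|
| 1, bilirubin limb | 1 ≥ 2? | Not met | Not met |
| 1, INR limb | 4 ≥ 3 and 2.5 > 1.5? | Met | Does not apply |
| 2 | 4 ≥ 5? | Not met | Not met |
| 3 | Hepatitis or hypersensitivity symptoms? | Not met | Not met |
| 4 | ALT ≥3×ULN for ≥4 weeks? | Not met | Not met |
| 5 | Weekly monitoring impossible? | Not met | Not met |
| Criteria met | | 1 of 5: stop | 0 of 5: continue under 5.7.6.2 |

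**Range.** The documents give no therapeutic INR range, so 2.5 is an assumption. Any INR above 1.5 with any ALT from 3 to below 5×ULN gives the same result. At INR ≤1.5 the two versions agree. Outside the band (bilirubin ≥2×ULN, ALT ≥5×ULN, symptoms, 4 weeks or more, or no weekly monitoring) treatment stops either way.

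**Follow-up duties also diverge.** Under Section 7.3.1.6 with footnote 3 applied, this subject falls in the reporting row for ALT ≥3 and <5×ULN with bilirubin <2×ULN. That row requires 24-hour notification but no Liver Event CRF unless the elevation persists or weekly monitoring fails. Under Section 5.7.6.1 the same subject has met criterion 1, which calls for the Liver Event CRF, an attempt to bring the subject back within 24 hours, and twice-weekly monitoring.

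**The case against.** The strongest reply has five parts.

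1. **Unseen figure.** Section 5.7.6.2 refers to the Appendix 3 algorithm, which is not visible in the text reviewed and may state the exemption. This stands as a caveat. The claim is about the wording of criterion 1. If the figure does carry the exemption, text and figure disagree on a stopping rule and the text still needs correcting.

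2. **Intent is clear.** The exemption appears three times, once within 5.7.6.1, so an investigator may read it across. That is plausible, but the text does not say to, and Section 3 allows no waivers except for immediate safety concerns.

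3. **The omission is conservative.** A stopping rule may be wider than an SAE definition. That is true in general: criteria 2–5 stop treatment without defining protocol-specific SAEs. But nothing in the protocol explains why an INR discounted for classification and reporting should decide stopping.

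4. **The exemption is broad.** It would also cover subjects on low-molecular-weight heparin or low-dose warfarin, in whom a raised INR need not be a drug effect. This is a fair point, and it applies equally to the three places where the sponsor already uses that wording.

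5. **Few subjects are affected.** On-study therapeutic warfarin needs medical monitor approval under Section 6.3, and liver stopping events reach the sponsor within 24 hours, so an unnoticed misapplication is less likely. The SAP (Sections 1.2 and 3.1) reports termination with 6 enrolled, and nothing shows that any of them fell in the band. The documents also do not say how often INR was tested outside the schedule in other subjects. All of this limits the practical impact; none of it makes the rule consistent.

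**Conclusion.** The concern holds. As written, criterion 1 permanently stops anticoagulated subjects whom the protocol would otherwise keep on treatment under weekly monitoring, on the strength of an INR it elsewhere disregards. For them, the ALT threshold for immediate stopping is 3×ULN where it would be 5×ULN with the exemption.

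The effect is confined to subjects who meet all of these conditions: receiving an anticoagulant, INR >1.5, ALT from 3 to below 5×ULN, bilirubin <2×ULN, no hepatitis or hypersensitivity symptoms, elevation under 4 weeks, and weekly monitoring possible. The documents do not give their number. It is probably very small among up to 30 planned subjects, and smaller still among the 6 enrolled.

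No loss of primary pharmacokinetic data follows: subjects who stop before surgery are replaced (Sections 4.1.1 and 5.3), and later stops come after the day-of-surgery samples. The statistical analysis is unaffected. The conclusion assumes that criterion 1 is applied as worded and that Appendix 3 does not override it.

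**What to change.** In Section 5.7.6.1, after the INR condition in criterion 1, add that the INR threshold is not applied to subjects receiving anticoagulants, in the terms already used in footnote 3 of Section 7.3.1.6. Then check that the Appendix 3 algorithm says the same. Section 5.7.6.2 needs no change, because it has no INR term. The bilirubin limb and criteria 2–5 remain in force for these subjects.

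If the sponsor prefers a narrower exemption, for example warfarin only, the change should be made in all four places together.

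The cost is one clause and one check of a figure, with no new data, visits or staff.

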**When any of the liver chemistry stopping criteria 1 - 5 is met, do the following:**

- **Immediately discontinue** investigational product
- Report the event to GSK within **24 hours** of learning its occurrence
- Complete the liver event case report form (CRF) and serious adverse event (SAE) data collection tool if the event also meets the criteria for an SAE
  - All events of ALT  $\geq 3xULN$  **and** bilirubin  $\geq 2xULN$  (>35% direct bilirubin) (or ALT  $\geq 3xULN$  and INR  $>1.5$ , if INR measured; INR measurement is not required and the threshold value stated will not apply to subjects receiving anticoagulants), termed ‘Hy’s Law’, **must be reported as an SAE (excluding studies of hepatic impairment or cirrhosis)**.
  - **NOTE:** If serum bilirubin fractionation is not immediately available, and if ALT  $\geq 3xULN$  **and** bilirubin  $\geq 2xULN$ , discontinue subject from study treatment. Serum bilirubin fractionation should be performed if testing is available. If testing is unavailable, **record presence of detectable urinary bilirubin on dipstick**, indicating direct bilirubin elevations and suggesting liver injury

- Complete the liver imaging and/or liver biopsy CRFs (provided by GSK) if these tests are performed
- Perform liver event follow up assessments, and monitor the subject until liver chemistries resolve, stabilize, or return to baseline values as described below
- Withdraw the subject from the study (unless further safety follow up is required) after completion of the liver chemistry monitoring as described below.
- For studies where survival or progression is an endpoint, follow-up for overall survival or progression is required following discontinuation from study treatment.
- Do not rechallenge with investigational product.

In addition, for subjects meeting liver stopping criterion 1:

- Make every reasonable attempt to have subjects return to clinic **within 24** hours for repeat liver chemistries, liver event follow up assessments (refer to Section 5.7.6.3), and close monitoring
- A specialist or hepatology consultation is recommended
- Monitor subjects twice weekly until liver chemistries (ALT, AST, alkaline phosphatase, bilirubin) resolve, stabilize or return to within baseline values.

In addition, for subjects meeting any of the criteria 2 - 5:

- Make every reasonable attempt to have subjects return to clinic within **24-72 hrs** for repeat liver chemistries and liver event follow up assessments (refer to Section 5.7.6.3)
- Monitor subjects weekly until liver chemistries (ALT, AST, alkaline phosphatase, bilirubin) resolve, stabilize or return to within baseline values;
  - Subjects meeting criterion 5 should be monitored as frequently as possible.

